8.4.2. Concomitant Medications and Procedures

Concomitant medications and procedures are defined as medications and procedures, such as surgeries, that were either initiated before the first dose of study drug and continued during the study treatment, or initiated on/after the date of the first dose of study drug and on/before 28 days after the end of the study treatment.

Concomitant medications collected on the “Prior and Concomitant Medication” eCRF page and concomitant procedures collected on the “Prior and Concomitant Procedures” eCRF page will be summarized for the Safety Population by tumor type/disease indication and in aggregate.

Concomitant anticancer therapies / medications will be summarized, if applicable, based on the therapeutic drug class ATC level 1 and preferred name, both based on WHODD March 2018 or later, sorted by frequency of ATC level 1 term and by preferred name within ATC level 1 terms, in the aggregate column; if counts tie, then further by alphabetical order. A table summarizing number of concomitant therapies and types of therapies will also be provided.

Concomitant procedures will be summarized, if applicable, based on the MedDRA, version 21.0 or higher, SOC and PT sorted by frequency of SOC and PT within SOC, in the aggregate column; if counts tie, then further by alphabetical order. A table summarizing number of concomitant procedures and types of therapies will also be provided.

Individual listings of concomitant medications and procedures will be provided to support the tables.

8.4.3. Subsequent Medications and Procedures

Subsequent medications, therapies and procedures, such as surgeries and transplants, are defined as medications or procedures that were started after the last dose of study treatment. A summary showing the number and percentage of subjects who took subsequent medications will be presented for the Safety Population by tumor type/disease indication and in aggregate.

Subsequent anticancer therapies collected on the “Anticancer Therapies for Brain Tumor - Systemic”, “Anticancer Therapies for Brain Tumor - Hormonal”, “Anticancer Procedures for Brain Tumor - Radiation Therapies”, “Anticancer Procedures for Brain Tumor - Cancer Surgeries”, and “Anticancer Procedures for Brain Tumor - Stem Cell Transplant” eCRF pages will be summarized.

The number of subsequent therapies and procedures, such as surgeries, will be summarized for subsequent radiation therapies, subsequent cancer surgeries, subsequent systemic anticancer therapies, subsequent stem cell transplants and other subsequent anticancer therapies by frequency tabulations based on the Safety Population. Descriptive statistics may be provided also, if needed. The therapies/surgeries with the same sequence/regimen number are counted as 1 subsequent therapy/surgery.

Subsequent anticancer therapies / medications will be summarized, if applicable, based on the therapeutic drug class (ATC level 1) and preferred name, both based on WHODD March 2018 or later, sorted by frequency of ATC level 1 term and by preferred name within ATC level 1 terms,

in the aggregate column; if counts tie, then further by alphabetical order. A table summarizing number of prior therapies and types of therapies will also be provided.

Subsequent procedures will be summarized, if applicable, based on the MedDRA, version 21.0 or higher, SOC and PT sorted by frequency of SOC and PT within SOC, in the aggregate column; if counts tie, then further by alphabetical order.

Individual listings of concomitant medications and procedures will be provided to support the tables.

9. STUDY TREATMENTS AND EXTENT OF EXPOSURE

Study treatment and extent of exposure summaries will be provided based on the Safety Population. Descriptive statistics (n, mean, median, StdDev, Q1, Q3, Min, and Max) will be provided for the following pomalidomide exposure parameters: treatment duration, cumulative dose, dose exposure, average daily dose, dose intensity and relative dose intensity. Total number, percentage, and frequency of cycles initiated, total number of doses administered, and dose reduction/interruption will also be presented.

Tables will present data by tumor type/disease indication, and in aggregate, split by cycle and overall across cycles.

Individual subject listings of exposure to study drug will be provided.

9.1. Treatment Duration

The treatment duration (days) is defined as:

$[(\text{date of last study drug administration}) - (\text{date of first study drug administration}) + 1]$; if in last cycle and 21 days of dose administered then cycle considered complete and date of last dose adjusted to include an additional 7 days, i.e. date of last dose + 7.

Note, the last cycle relates to the last cycle a given subject received before discontinuing from the study Treatment Period.

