7.2. Treatment Administration and Schedule

The starting dose of pomalidomide will be 2.6 mg/m²/day, based on the subject's actual BSA calculated at the beginning of each cycle. Pomalidomide (oral capsules or suspension) will be administered daily for the first 21 days of every 28-day cycle and only enough pomalidomide for 1 cycle (21-day supply) of treatment will be dispensed on Day 1 of each new cycle of therapy. The oral suspension is available for use in subjects who are unable to swallow the capsules or at the discretion of the Investigator. On Day 1 of each cycle, pomalidomide will be dispensed and administered after completion of all clinical procedures required for that day. Subsequent pomalidomide administration (ie, Days 2-21 of each cycle) may occur at the subject's home.

Pomalidomide will not be administered on Days 22 through 28 of the 28-Day treatment cycle even if a subject experiences a toxicity that requires dose interruption (see Section 7.2.2). Counting of days should continue uninterrupted and the rest period (Days 22 to 28) should be continued as planned. For example, if a subject experiences a toxicity that requires interruption and does not recover until Day 22, pomalidomide should be restarted on Day 1 of the subsequent cycle if other protocol parameters are met. Subjects will continue treatment for up to 24 cycles or until documented PD, withdrawal of consent/assent, treatment becomes intolerable or death, whichever comes first.

For subjects receiving capsules, the pomalidomide dose should be calculated and rounded up or down to the nearest 0.5 mg as the prescribed dose before each new dosing cycle. The dose

prescribed should be based on the subject's BSA and yield the minimum number of capsules to achieve the prescribed dose. However, if a subject is unable to swallow larger capsules, varying appropriate strength combinations may be considered during medication assignment.

Pomalidomide capsules should not be broken, chewed or opened and should be taken at approximately the same time every day for 21 consecutive days in a cycle. If a dose is vomited within 15 minutes of taking the dose and the capsule(s) are visible in the emesis, the dose should be repeated and the Investigator should be notified to have replacement capsule(s) provided. If vomiting occurs beyond 15 minutes of dosing, do not repeat the dose and that day's dose should be skipped. Any vomiting of the capsules should be described in the subject dosing diary.

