7.2.1. Criteria for Starting Subsequent Treatment Cycles

Prior to the start (within 48 hours) of each treatment Cycle (Day 1) the following parameters **MUST** be met:

- ANC \geq 1,000/mm³
- Platelet count \geq 100,000/mm³ (transfusion independent, defined as no platelet transfusion within 7 days and recovery from nadir)
- Does not meet PD or treatment interruption/discontinuation criteria

In addition, subjects **MUST** meet the following within 24 hours prior to the start of each treatment cycle:

- Confirmation of negative serum or urine pregnancy test (sensitivity of at least 25 mIU/mL) in FCCBP/FCBP.
- Confirmation of the use of 2 forms of effective birth control for FCCBP/FCBP and sexually mature males or confirmation of commitment to complete abstinence.
- Completion and documentation of required pomalidomide education and counseling.

If a subject does not meet the above parameters by Day 28 of a treatment cycle, then the subsequent cycle should not be started until these parameters are met. Refer to Section 7.2.2 for dose interruptions/reductions or next cycle delays due to count recovery or non-hematological toxicities.

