7.2.2.1. Dose Modifications

Table 8: Dose Modification Criteria

Toxicity	Dose Modification and Discontinuation
Grade 4 neutropenia that occurs during the 21-day dosing period Grade 3 or 4 febrile neutropenia Grade 4 neutropenia of ≥ 5 days duration during the treatment rest period	
 • Interrupt pomalidomide until the neutrophil count recovers to ≥ 1000/mm³ and no fever (≤ 38.3 °C) (if applicable). • If the toxicity resolves and the subject meets eligibility parameters to resume as described in the protocol within 14 days (eg, ANC ≥ 1000/mm³; platelets ≥ 100,000/mm³), the subject should re-initiate treatment at one dose level lower. • If the dose modifying toxicity does not resolve to meet the parameters as described in the protocol within 14 days of treatment being held, pomalidomide should be permanently discontinued.
Grade 3 or 4 platelet count decreased that occurs during the 21 day dosing period	
 • Transfuse platelets to a post-transfusion plate target of ≥ 100,000/μL if platelet count is < 50,000/mm³. • Interrupt pomalidomide until the platelet count recovers to ≥ 100,000/mm³ unsupported (defined as no platelet transfusion within 7 days and recovery from nadir). • If the toxicity resolves and the subject meets eligibility parameters to resume as described in the protocol within 14 days (eg, ANC ≥ 1000/mm³; platelets > 100,000/mm³), the subject should re-initiate treatment at one dose level lower. • If the toxicity does not resolve to meet the eligibility parameters as described in the protocol within 14 days of treatment being held, pomalidomide should be permanently discontinued.

Table 8: Dose Modification Criteria (Continued)

Toxicity	Dose Modification and Discontinuation

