11. DISCONTINUATIONS

11.1. Treatment Discontinuation

The following events are considered sufficient reasons for discontinuing a subject from the IP(s):

- Adverse Event
- Withdrawal of consent/assent by subject/parent(s)/legal guardian(s) - under this situation, the Investigator should clarify if the family also wishes to withdraw the study ICF/IAF for continued participation in the Long-term Follow-up Period and data collection
- Death
- Lost to follow-up
- Pregnancy
- Non-compliance with IP
- Progressive disease
- Physician decision
- Protocol violation
- Completion of the Treatment Period (24 cycles)
- Study or site terminated by Sponsor
- Other (to be specified on the eCRF)

The reason for discontinuation of treatment, last dose of treatment and date subject taken off treatment should be recorded in the eCRF and in the source documents.

The decision to discontinue a subject from treatment remains the responsibility of the treating physician and will not be delayed or refused by the Sponsor. However, prior to discontinuing a subject, the Investigator may contact the Medical Monitor and forward appropriate supporting documentation for review and discussion.

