9.5. Average Dose Intensity

The daily average dose intensity ($\text{mg}/\text{m}^2/\text{day}$) is calculated as:

$$\text{Cumulative Dose} / \text{Treatment Duration.}$$

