9.6. Relative Dose Intensity

Relative Dose Intensity is calculated as:

$$\text{Average Dose Intensity} / \text{Planned Dose Intensity.}$$

The pomalidomide planned dose intensity (PDI) is calculated as $(2.6 \text{ mg/m}^2 * 21) / 28$.

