9.7. Dose Modifications - Reduction/Interruption/Delay/Discontinuation

Dose reductions are identified as an actual scheduled dose as recorded on the study drug record eCRF page, eg, $> 0 \text{ mg/m}^2$, while being less than the scheduled dose directly prior to the current administration.

If an interruption happens at the start of a cycle and causes the cycle start to be delayed, it is also called a dose delay. Dose delays will be considered together with dose interruptions. Drug interruption are identified as a non-administered planned dose, eg, planned dose $> 0 \text{ mg/m}^2$ while actual dose received = 0 mg/m^2 , while being directly followed with an actual administered dose eg, actual dose received $> 0 \text{ mg/m}^2$, provided an actual dose had been administered previously, ie, a delay will be identified on Day 1 for Cycle 2 onwards provided Cycle 2 onwards had at least one drug administration. Drug interruptions are identified as the time between Day 1 of a current cycle and the last actual dose date of the preceding cycle being > 8 days.

Dose discontinuations are identified as being where the planned dose is $> 0 \text{ mg/m}^2$ while actual dose received = 0 mg/m^2 , and no further study dose administered.

The overall number and percentage of subjects who have at least one dose reduction/interruption/discontinuation of pomalidomide will be provided for each reason given. Time to first dose reduction/interruption/discontinuation due to any reason will be descriptively provided. Time to first dose reduction/interruption due to AE will also be descriptively provided (n, mean, median, StdDev, Q1, Q3, Min, and Max).

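### Average and relative dose intensity come out too high when the last cycle stops before Day 21, because the duration omits that cycle's share of the rest week and planned intensity includes it

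*SAP*

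**What the plan says.** Dosing runs on Days 1 to 21 of each 28-day cycle. Protocol 7.2 states: "Pomalidomide will not be administered on Days 22 through 28 of the 28-Day treatment cycle".

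SAP Section 9 builds the exposure measures in steps:

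- **9.1, treatment duration:** last dose date minus first dose date plus 1. Seven days are added only where the last cycle qualifies as complete: "if in last cycle and 21 days of dose administered then cycle considered complete and date of last dose adjusted".
- **9.3, cumulative dose:** the sum of all doses taken, in mg/m².
- **9.5:** "The daily average dose intensity" is cumulative dose divided by the 9.1 duration.
- **9.6:** RDI is average dose intensity divided by planned dose intensity. "The pomalidomide planned dose intensity (PDI) is calculated as" 2.6 mg/m² times 21, divided by 28.

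The introduction to Section 9 asks for these summaries in the Safety Population, by tumor type and in aggregate, split by cycle and overall. Appendix A2, Section 3, defines cycle and treatment end dates differently, but 9.5 uses the 9.1 duration. Nothing else in Section 9 deals with an incomplete last cycle.

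**The concern.** A planned intensity of 1.95 mg/m²/day spreads 21 doses over 28 days, so each planned day carries its share of the rest week. The actual intensity must be computed over a duration built the same way. For every cycle before the last this happens automatically, because the rest week and any delay fall before the final dose. For a complete last cycle the added 7 days do the job. For an incomplete last cycle nothing does.

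A subject who took no more than the planned dose is then reported above 100%. The excess is greatest for those who stop earliest, and these subjects remain in the Safety Population. In Cycle 1 a subject with 20 doses scores 133.3% and one with all 21 scores 100%. In strata of 9 to 20 subjects, one value of 133.3% among subjects otherwise at 100% lifts the mean by 33.3/9 = 3.7 points or 33.3/20 = 1.7 points, and sets the maximum. A reader using RDI to judge how well the dose was tolerated would be misled.

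**Working it through.** **Inputs.** Dose 2.6 mg/m²/day (Protocol 7.2; SAP 9.6); 21 dosing days in a 28-day cycle; duration, intensity and RDI as in SAP 9.1, 9.5 and 9.6. Planned intensity = 2.6 × 21 / 28 = 1.95 mg/m²/day.

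**Check of the SAP's own rule.** The SAP states no RDI value to reproduce. For k complete cycles without gaps, dose = 54.6k, duration = 28k (with the 7 days added), and RDI = (54.6/28)/1.95 = 100%. The rule works when the last cycle is complete.

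**Stop on Day d (1 to 20) of Cycle k, full dose, no gaps.** Cumulative dose = 2.6 × [21(k−1) + d]; duration = 28(k−1) + d. Since 1.95/2.6 = 0.75,

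RDI = {[21(k−1) + d] / [28(k−1) + d]} / 0.75.

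| Last cycle | Stop on Day 1 | Stop on Day 20 |
|---|---|---|
| 1 | (1/1)/0.75 = 133.3% | (20/20)/0.75 = 133.3% |
| 2 | (22/29)/0.75 = 101.1% | (41/48)/0.75 = 113.9% |
| 6 | (106/141)/0.75 = 100.2% | (125/160)/0.75 = 104.2% |
| 24 | (484/645)/0.75 = 100.05% | (503/664)/0.75 = 101.0% |

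The value should be 100% throughout. In Cycle 1 the average dose intensity itself is 2.6 instead of 1.95 mg/m²/day.

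**One missed dose, last dose on Day 21 of Cycle 1.** The 21-day condition can be read two ways. If it means 21 actual doses, 20 doses earn no extra days: (52/21)/1.95 = 127.0%. If it means that dosing reached Day 21, the result is (52/28)/1.95 = 95.2%.

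**Delay.** Protocol 7.2.1 allows late starts: if the criteria are not met, "then the subsequent cycle should not be started until these parameters are met". Take a 7-day delay before Cycle 2 and a stop on Day 10 of it. Dose = 2.6 × 31 = 80.6.

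- SAP: duration 28 + 7 + 10 = 45; (80.6/45)/1.95 = 91.9%.
- With the rest share: duration 35 + (28/21) × 10 = 48.33; (80.6/48.33)/1.95 = 85.5%.

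**Reductions (arithmetic illustration).** One cycle at 2.6, two at 1.9, stop on Day 14 of Cycle 4 at 1.3. Dose = 54.6 + 79.8 + 18.2 = 152.6.

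- SAP: (152.6/98)/1.95 = 79.9%.
- With the rest share: duration 84 + (28/21) × 14 = 102.67; (152.6/102.67)/1.95 = 76.2%.

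In the last two cases RDI is below 100% but still too high.

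**The case against.** **Practical weight.** RDI feeds no endpoint or stage decision. Cumulative dose, dosing days, number of doses, cycles initiated and dose modifications are all reported separately and are correct. Protocol 3.1 and 6.2 place scheduled scans on Day 1 or in the preceding 7 days, so progression found on a scheduled scan after full dosing falls after Day 21, where the SAP gives exactly 100%. The no-gap excess is at most 4.2 points by Cycle 6 and 1.0 by Cycle 24. All of this stands and limits the point. It does not make the formula right for a mid-cycle stop, whose frequency the documents do not give.

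**A stronger reading.** A reader might infer that days held after the last dose are also wrongly left out. Protocol 7.2.2.1 provides for toxicity that has not resolved "within 14 days of treatment being held, pomalidomide should be permanently discontinued". A subject dosed on Days 1 to 10 of Cycle 1, held, and discontinued on Day 24 scores 133.3% under the SAP; counting the held days against the 21 planned doses would give 26/54.6 = 47.6%.

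The documents do not support calling that omission an error. SAP 9.1 deliberately ends duration at the last dose, and 9.7 takes the same view: "Dose discontinuations are identified as being where the planned dose is" above zero, none is received and no further dose follows. A hold with no later dose is therefore a discontinuation, and counting its days is a choice of convention. It would also make RDI for the same 10 doses depend on the recorded off-treatment date: 100% for an outright stop, 26/(2.6 × 12) = 83.3% if taken off on Day 12, and 47.6% on Day 24. What stands for this subject is the missing rest share: 133.3% where 100% is consistent with the SAP's own end point.

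**Conclusion.** As written, SAP 9.1, 9.5 and 9.6 together overstate average and relative dose intensity whenever the last cycle stops on Days 1 to 20. At full dose with no gaps the excess is 33.3 percentage points in Cycle 1, 1.1 to 13.9 in Cycle 2, 0.2 to 4.2 in Cycle 6 and at most 1.0 in Cycle 24. Stops after all 21 doses are unaffected.

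The figures assume that recorded doses equal the stated mg/m² level, ignoring capsule rounding. The 127.0% result also depends on reading the 21-day condition as 21 actual doses. It would be wrong to conclude that every RDI exceeds 100%, that held days after the last dose are an error, or that any efficacy result is touched. The point is worth correcting before database lock because the rule gives a wrong value and the repair is small.

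**What to change.** Replace the conditional 7 days with one schedule-adjusted duration, used in both 9.5 and 9.6:

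(days from first dose to the day before Day 1 of the last cycle received) + (28/21) × min(21, days from Day 1 of the last cycle to the last dose, both included).

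Keep average dose intensity as cumulative dose divided by this duration, and RDI as that intensity divided by 1.95, so the two measures stay consistent.

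Behaviour of the rule:

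- Complete last cycle: (28/21) × 21 = 28 days, unchanged. A 7-day delay followed by a complete Cycle 2 stays at (109.2/63)/1.95 = 88.9%.
- Adherent stop on Day 10 of Cycle 1: 26/13.33 = 1.95, so 100%.
- One dose missed before Day 21, last dose on Day 21 of a single cycle: (52/28)/1.95 = 95.2%, with no need to interpret the 21-day condition.

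For the by-cycle tables, state that earlier cycles use the Appendix A2 cycle window and the last cycle uses this rule. Do not add held days after the last dose.

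**Cost.** SAP wording and one derivation. No new data: Appendix A2 takes Day 1 of each cycle from the eCRF, and Protocol 11.1 says that "last dose of treatment and date subject taken off treatment should be recorded in the eCRF".

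**Downsides.** Reported RDI becomes slightly less favourable. Doses missed at the very end of the last cycle are still not counted: if only the Day 21 dose is missed, duration is (28/21) × 20 = 26.67 and RDI is (52/26.67)/1.95 = 100%. Dosing days, cumulative dose and the listings show what was taken.

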9.2. Dose Exposure

Dose exposure (days) is defined as the total number of actual drug administration days.

9.3. Cumulative Dose

The cumulative dose (mg/m^2) is defined as the sum of all doses taken across the Treatment Period.

9.4. Average Daily Dose

Average daily dose will be calculated as:

$$\text{Cumulative Dose} / \text{Dose Exposure.}$$

9.5. Average Dose Intensity

The daily average dose intensity ($\text{mg}/\text{m}^2/\text{day}$) is calculated as:

$$\text{Cumulative Dose} / \text{Treatment Duration.}$$

9.6. Relative Dose Intensity

Relative Dose Intensity is calculated as:

$$\text{Average Dose Intensity} / \text{Planned Dose Intensity.}$$

The pomalidomide planned dose intensity (PDI) is calculated as $(2.6 \text{ mg/m}^2 * 21) / 28$.

9.7. Dose Modifications - Reduction/Interruption/Delay/Discontinuation

Dose reductions are identified as an actual scheduled dose as recorded on the study drug record eCRF page, eg, $> 0 \text{ mg/m}^2$, while being less than the scheduled dose directly prior to the current administration.

If an interruption happens at the start of a cycle and causes the cycle start to be delayed, it is also called a dose delay. Dose delays will be considered together with dose interruptions. Drug interruption are identified as a non-administered planned dose, eg, planned dose $> 0 \text{ mg/m}^2$ while actual dose received = 0 mg/m^2 , while being directly followed with an actual administered dose eg, actual dose received $> 0 \text{ mg/m}^2$, provided an actual dose had been administered previously, ie, a delay will be identified on Day 1 for Cycle 2 onwards provided Cycle 2 onwards had at least one drug administration. Drug interruptions are identified as the time between Day 1 of a current cycle and the last actual dose date of the preceding cycle being > 8 days.

Dose discontinuations are identified as being where the planned dose is $> 0 \text{ mg/m}^2$ while actual dose received = 0 mg/m^2 , and no further study dose administered.

The overall number and percentage of subjects who have at least one dose reduction/interruption/discontinuation of pomalidomide will be provided for each reason given. Time to first dose reduction/interruption/discontinuation due to any reason will be descriptively provided. Time to first dose reduction/interruption due to AE will also be descriptively provided (n, mean, median, StdDev, Q1, Q3, Min, and Max).

